8.1 Pre-randomisation/Screening Assessments – ALL ARMS

The following assessments must be performed 28 days prior to randomisation (unless otherwise specified):

- Informed consent
- Assessment of PD-L1 expression on new (fresh) biopsy sample or archival tissue
- Review of inclusion and exclusion criteria
- Demographics
- SINS score for spinal lesions (if applicable i.e. known spinal metastases)
- Comprehensive medical history (including disease specific medical history)
- Physical examination
- Vital signs and body measurements
- Documentation of prior medications at time of screening
- Documentation of ECOG performance status
- Radiological evaluation with a CT Brain, Chest/Abdomen and Pelvis or MRI must be performed within 6 weeks of randomisation
- Whole body bone scan (if clinically indicated) within 6 weeks of randomisation
- FDG-PET scan
- Laboratory studies no more than 10 days prior to randomisation including FBE, biochemistry and coagulation, hepatic, kidney and thyroid function tests
- Virology (HIV, Hepatitis B and C) within 21 days prior to randomisation, if clinically indicated
- Pregnancy test in female patients with child bearing potential within 7 days prior to randomisation

- New (fresh) biopsy sample within 12 weeks of randomisation, if applicable
- Blood samples for correlative studies

8.2 Treatment Phase - ARM 1 (SABR followed by pembrolizumab)

8.2.1 SABR Visit Assessments

The following assessments must be performed prior to the first dose of SABR:

- Documentation of concomitant medications
- Blood samples for correlative studies

8.2.2 Cycle 1 Assessments

The following assessments must be performed 7 days \pm 2 days after the last dose of SABR:

- Physical examination
- Vital signs and weight
- Documentation of concomitant medications
- Documentation of ECOG performance status
- Laboratory studies including FBE, biochemistry and coagulation, hepatic, kidney and thyroid function tests
- Pregnancy test in female patients with child bearing potential.
- Blood samples for correlative studies

8.2.3 Cycle 2 to Cycle 34 Assessments

The following assessments will be performed within 3 days prior to pembrolizumab dosing in each cycle, unless otherwise specified.

- Physical examination
- Vital signs and weight
- Documentation of concomitant medications
- Documentation of ECOG performance status
- Laboratory studies including FBE, biochemistry and coagulation, hepatic and kidney
- Thyroid function tests (every 6 weeks)
- Radiological evaluation with a CT Chest/Abdomen and Pelvis or MRI (prior to cycle 3, 5, 7 and every 3 cycles thereafter)
- FDG-PET scan prior to cycle 5
- Whole body bone scan (prior to cycle 3, 5, 7 and every 3 cycles thereafter, only if clinical indicated)
- Response assessment (prior to cycle 3, 5, 7 and every 3 cycles thereafter)
- Adverse events assessment
- Pregnancy test in female patients with child bearing potential.
- Blood samples for correlative studies

8.3 Treatment Phase - ARM 2 (pembrolizumab followed by SABR)

8.3.1 Cycle 1 Assessments

The following assessments must be performed within 3 days prior to the first dose of pembrolizumab in cycle 1:

- Physical examination
- Vital signs and weight
- Documentation of concomitant medications
- Documentation of ECOG performance status
- Laboratory studies including FBE, biochemistry and coagulation, hepatic and kidney function tests
- Pregnancy test in female patients with child bearing potential.
- Blood samples for correlative studies

8.3.2 SABR Visit Assessments

The following assessments will be performed at the SABR visit, 7 days from Cycle 1 Day 1 (\pm 2 days):

- Documentation of concomitant medications
- Blood samples for correlative studies

8.3.3 Cycle 2 to Cycle 34 Assessments

The following assessments will be performed within 3 days prior to pembrolizumab dosing in each cycle, unless otherwise specified:

- Physical examination
- Vital signs and weight
- Documentation of concomitant medications
- Documentation of ECOG performance status
- Laboratory studies including FBE, biochemistry and coagulation, hepatic and kidney
- Thyroid function tests (every 6 weeks)
- Radiological evaluation with a CT Chest/Abdomen and Pelvis or MRI (prior to cycle 3, 5, 7 and every 3 cycles thereafter, only if clinical indicated)
- FDG-PET scan prior to cycle 5
- Whole body bone scan (prior to cycle 3, 5, 7 and every 3 cycles thereafter, only if clinical indicated)
- Response assessment (prior to cycle 3, 5, 7 and every 3 cycles thereafter, only if clinical indicated)
- Adverse events assessment
- Pregnancy test in female patients with child bearing potential.
- Blood samples for correlative studies

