Trial Phase:	Screening Phase	Treatment Phase			Follow-up Phase		Progression
Trial phase and windows	Screening -28 to -1	Day 1 Cycle 1 3 days \pm 2 days prior to the first dose of pembrolizumab	SABR 7 days \pm 2 days from cycle 1 day 1	Day 1 Cycle 2-34 3 days \pm 2 days prior to each dose of pembrolizumab	Safety Follow-up 30 days \pm 3 days from date of last dose of pembrolizumab	Follow-up 3 months \pm 7 days from the last cycle of pembrolizumab	Upon first progression ¹
Biochemistry ⁶	X	X		X		indicated	
Thyroid Function tests ⁷	X	X		X			
Coagulation profile ⁸	X	X		X			
Virology ⁹	X						
Tumour Evaluation							
CT scan (Brain, Chest, Abdo, Pelvis) reported with RECIST 1.1 or MRI ¹⁰	X			X		X	
Whole body bone scan ¹⁰ (if clinically indicated)	X			X		X	
Response assessment ¹⁰				X		X	
FDG-PET ¹⁰	X			X ¹¹			
Translational studies							
Fresh tumour biopsy sample ¹²	X					X	X
Archival tumour biopsy sample ¹³	X						
Blood Collection ¹⁴ (serum and ctDNA)		X	X	X		X	X

Table 1 and 2 Footnotes

1. Beyond first progression, every effort should be made to record results of subsequent tumour assessments. In addition, details of any new anti-cancer treatment commenced is to be collected.
2. Vital signs include blood pressure, heart rate, respiratory rate and temperature. Body measurements including height and weight (height only required at screening).
3. Urine or serum pregnancy test for patient of childbearing potential should be performed within 7 days randomisation and also 72 hours before first dose of pembrolizumab. If the urine test is positive or cannot be confirmed as negative, a serum pregnancy test will be required.
4. Baseline abnormalities must be recorded from signature of informed consent to prior to start of treatment. Adverse events (using CTCAE v4.03) are then required to be reported on completion of SABR, day 1 of every pembrolizumab cycle and at every follow-up visit. If at any time, a patient commences a new anti-cancer therapy, recording of adverse events is no longer required.

Laboratory Procedures/Assessments – All diagnostic laboratory tests should be performed within 10 days of randomisation (to determine eligibility), and also on day 1 ± 3 days of every cycle of pembrolizumab (unless otherwise specified)

5. Haematology: Haematocrit, haemoglobin, platelet count, white blood cell count (total and differential), red blood cell count, absolute neutrophil count and absolute lymphocyte count.

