6. Biochemistry: calcium chloride, glucose, phosphorus, potassium, sodium, magnesium, total protein, Liver Function Tests: Albumin, Alkaline Phosphatase (ALP), Alanine Aminotransferase (ALT), Aspartate Aminotransferase (AST), Lactate Dehydrogenase (LDH), Gamma-Glutamyl Transferase (GGT), total bilirubin (+direct bilirubin if total bilirubin is elevated above the ULN), Kidney Function Tests: Urea, creatinine.
7. Thyroid Function tests: T3, T4 and TSH. To be performed at during screening, day 1 cycle and every 6 weeks thereafter.
8. Coagulation Profile: PT (INR), aPTT.
9. Virology: HIV, Hepatitis B and C tests only required for those patients at risk of prior or current active infection as determined by the investigator. To be performed within 21 days of randomisation.

Tumour evaluation

10. Radiological tumour assessments will be performed by CT scan (or MRI as required if tumour is in extremity) at screening (within 6 weeks of randomisation), prior to cycle 3, 5, 7 and every 3 cycles thereafter in the treatment phase. Then 3 monthly in the follow-up phase until the last patient recruited completes 24 months of follow-up, unless evidence of progression earlier. Whole body bone scan (WBBS) will be performed if clinically indicated at the same time points. Formal response assessment (using RECIST 1.1, irRECIST, Peter Mac Metabolic Response Criteria and PERCIST 1.0.) at each scheduled scan time point. Response should be confirmed with repeat imaging 4 to 8 weeks later by the same imaging modality. CT of brain only required at screening.
11. FDG PET at baseline and prior to cycle 5 of pembrolizumab. (note: a contemporaneous CT brain/chest/abdo pelvis performed at the same time will fulfill the CT requirement 3 month follow-up)

Biological Evaluations

12. A fresh biopsy of the primary or metastatic lesion will be performed at screening (within 12 weeks of randomisation). and 3 months post completion of SABR. This will ideally be the same site as biopsied before at screening. In event of disease progression, a sample from progressing metastatic site(s), if feasible, is requested. Refer to the SABRseq laboratory manual for further details on handling and shipping of tumour samples.

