8.5 Follow-Up – All Arms

Patients who complete the treatment phase, or discontinue trial treatment for a reason other than disease progression will move into the follow-up phase. The following assessments will be performed every 3 months up until the last patient has completed 24 months of follow-up, until the start of new anti-neoplastic therapy, disease progression, death or end of the study.

- Physical examination
- Vital signs and weight
- Documentation of ECOG performance status
- Laboratory studies including FBE, biochemistry and coagulation, hepatic and kidney function tests (only if clinically indicated)
- Radiological evaluation with a CT Chest/Abdomen and Pelvis or MRI
- Whole body bone scan (only if clinical indicated)
- Response assessment
- Adverse Event assessment
- Blood samples for correlative studies
- New anti-cancer therapy status
- Fresh biopsy sample 3 months after the last dose of SABR if considered safe

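### Section 8.3.3 makes Arm 2 on-treatment CT/MRI and response assessment conditional on clinical indication, contradicting Table 2, footnote 10 and the Arm 1 text, so PFS and response could be ascertained differently by arm

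*Combined protocol and SAP*

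**What the plan says.** Two rules are given for imaging Arm 2 during treatment.

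- **Section 8.3.3 (Arm 2)** lists "CT Chest/Abdomen and Pelvis or MRI (prior to cycle 3, 5, 7 and every 3 cycles thereafter, only if clinical indicated" and "Response assessment (prior to cycle 3, 5, 7 and every 3 cycles thereafter, only if clinical indicated". The bone-scan bullet carries the same condition. The one on-treatment imaging item without it is "FDG-PET scan prior to cycle 5".
- **Section 8.2.3 (Arm 1)** lists "Response assessment (prior to cycle 3, 5, 7 and every 3 cycles thereafter" with no condition. Its CT/MRI bullet is also unconditional, and only the bone scan is qualified.
- **Section 3, Table 2 (Arm 2)** marks the row "CT scan (Brain, Chest, Abdo, Pelvis) reported with RECIST 1.1 or MRI" and the response row at cycles 2 to 34 without a qualifier.
- **Footnote 10, covering both arms,** requires tumour imaging "prior to cycle 3, 5, 7 and every 3 cycles thereafter in the treatment phase" and a formal response assessment at each of those scans. The condition is kept for one item: "Whole body bone scan (WBBS) will be performed if clinically indicated at the same time points".
- **Section 8.5 (follow-up, all arms)** has "Radiological evaluation with a CT Chest/Abdomen and Pelvis or MRI", again unconditional.

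Section 5.2 makes comparison of response and PFS between arms a secondary objective. Section 14.6 plans a stratified log-rank test and section 14.7 Fisher's exact test. Section 14.3 limits the response population to treated patients who were scanned at the visit in question.

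**The concern.** The two rules cannot both hold for Arm 2, and no precedence rule was found. The opening of section 8 refers the reader to the schedule table, while section 10 refers sites to sections 8.2 and 8.3 for what must be done before each dose. A site that worked from 8.3.3 could claim to be following the protocol.

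The difference would fall exactly along the randomised comparison, in an open-label trial.

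- **PFS.** Progression would be found on a fixed calendar in Arm 1 and mainly on clinical suspicion in Arm 2. Silent progression would tend to be dated later in Arm 2. Progression that prompts an early scan could be dated sooner. The log-rank test would compare two detection processes as well as two treatment sequences.
- **Response.** Section 14.7 reports response at 6 and 12 months after SABR starts. If Arm 2 scans depend on clinical judgement, so does the Arm 2 denominator under section 14.3, and Fisher's test no longer compares like with like.

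**Working it through.** **Plan's own figures.** The plan states no figure on this point. Its sample-size basis in section 14.9 reproduces (1 - 0.9^16 = 0.815 for a 10% toxicity) and does not depend on imaging.

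**Scans fixed by each rule.** Cycles last 3 weeks, so cycle c starts at week 3(c - 1). The required cycles are 3, 5, 7, 10, 13, 16, 19, 22, 25, 28, 31 and 34. These are weeks 6, 12, 18, 27, 36, 45, 54, 63, 72, 81, 90 and 99, or 12 assessments. Read literally, 12 are fixed in Arm 1 and 0 in Arm 2, apart from the PET at week 12. The CTs nearest to 6 and 12 months are cycle 10 (week 27) and cycle 19 (week 54), and both are conditional under 8.3.3.

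**PFS illustration.** The documents give no detection lag and no rate of unscheduled scanning, so the lags below are assumptions.

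- True progression is exponential and identical in both arms.
- True medians come from section 4.12: 3.0 months (previously treated), 6.0 months (previously untreated) and 10.3 months (first line, PD-L1 at least 50%, an upper case because this trial does not require that level).
- Arm 1 detection is at the next scheduled scan.
- Arm 2 detection is at the true time plus an exponential lag, and no later than week 12 if progression occurred by then (the cycle 5 PET).
- Every Arm 2 patient follows 8.3.3. Deaths and moves to 3-monthly follow-up CT are not modelled.

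Restricted-mean PFS to 24 months, Arm 2 minus Arm 1, in months:

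| True median | Lag 2 wk | 4 wk | 8 wk | 12 wk | 16 wk |
|---|---|---|---|---|---|
| 3.0 | -0.4 | -0.1 | +0.5 | +1.1 | +1.6 |
| 6.0 | -0.5 | -0.1 | +0.6 | +1.2 | +1.7 |
| 10.3 | -0.4 | -0.1 | +0.5 | +1.0 | +1.5 |

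The Arm 1 calendar itself delays detection by about 4 weeks on average. The sign changes at a mean Arm 2 lag of about 4.5 weeks. If half of Arm 2 follows 8.3.3, each difference halves.

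An unstratified log-rank test with 16 per arm and no true difference rejects in roughly 5% to 6% of trials when schedules are equal. With unequal schedules it rejects in about 6% to 14%. The highest value is for the 3.0-month median at a 16-week lag.

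**Response illustration.** Let p be the true response rate and q the fraction scanned in the under-scanned group, with everyone else scanned. The observed rate is:

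- responders under-scanned: pq / (pq + 1 - p)
- non-responders under-scanned: p / (p + (1 - p)q)

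The rates p are from section 4.12: 24.8% (previously untreated) and 18.0% (previously treated).

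| p | Under-scanned group | q = 0.75 | q = 0.50 | q = 0.25 |
|---|---|---|---|---|
| 24.8% | responders | 19.8% | 14.2% | 7.6% |
| 18.0% | responders | 14.1% | 9.9% | 5.2% |
| 24.8% | non-responders | 30.5% | 39.7% | 56.9% |

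For example, 0.248 × 0.50 / (0.248 × 0.50 + 0.752) = 0.124 / 0.876 = 14.2%.

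**The case against.** The strongest reply is that this is a copying slip. The two bullets name fixed cycles and then add the condition that belongs to the bone-scan bullet beside them. Most of the document points the other way. Besides Table 2, footnote 10 and section 8.5, section 6 has tumour response assessed in both arms, section 13.1 expects the screening modality to be used at every visit, and section 14.7 requires all response measurements to be recorded. Nothing shows that any site has followed 8.3.3. The intended reading is therefore fairly clear, but 8.3.3 is still a list that sites are told to work from.

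The zero count for Arm 2 is a worst case. Footnote 11 lets a CT done with the PET count towards the CT requirement, and patients who stop treatment without progression move to unconditional 3-monthly CT in both arms. This reduces the effect without removing it for patients still on treatment.

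The figures are driven by assumptions, and that stands. Deaths count as PFS events and do not depend on scans. If 30% of events were deaths (an assumption), the largest difference at a 6.0-month median would fall from +1.7 to about +1.2 months (1.73 × 0.7 = 1.21). The simulated log-rank test is unstratified, whereas the plan's is stratified.

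Toxicity is also not wholly insulated. Progression can end treatment (section 7.6), and adverse-event recording stops once new anti-cancer therapy starts (footnote 4). Different detection times could therefore alter exposure and follow-up. That is a minor, indirect route.

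**Conclusion.** The concern holds. The contradiction is in the text and needs no model to establish it. Any harm depends on sites having followed 8.3.3.

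If they did, the PFS and response comparisons would rest on different ascertainment by arm, in a direction the documents do not settle. In the PFS scenarios the shift lies between about -0.5 and +1.7 months. Those values assume full adherence to 8.3.3 and no deaths, so they sit at the upper end for the lags considered. Test error rises only modestly. The main risk is a distorted estimate in each arm, and for response the distortion can go either way.

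OS, the sample-size basis and the PET scan behind the interim analysis are unaffected. The primary toxicity endpoint is touched only by the indirect route above. The point should be fixed, but it does not threaten the trial's main purpose.

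**What to change.** Reconcile the CT/MRI and response-assessment bullets of section 8.3.3 with section 8.2.3, Table 2 and footnote 10, so that both arms share one on-treatment assessment schedule, and notify both sites. If any Arm 2 patient has already been assessed under the conditional wording, report scheduled against performed scans by arm alongside the PFS and response results. Scans that were not done cannot be recovered at analysis.

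The cost is a wording change to two bullets in an amendment and a notice to two sites. The assessments are already in Table 2 and footnote 10, so no procedure is added.

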8.4 Safety Follow-up – All Arms

The following assessments will be performed during the safety follow-up visit to be conducted approximately 30 days after the last dose of trial treatment or before the initiation of a new anti-cancer treatment, whichever comes first.

- Adverse events assessment: Patients with an AE of Grade > 1 will be followed until the resolution of the AE to Grade 0-1 or until the beginning of a new anti-neoplastic therapy, whichever occurs first. SAEs that occur within 30 days of the end of treatment or before initiation of a new anti-cancer treatment should also be followed and recorded.
- New anti-cancer therapy status.

8.5 Follow-Up – All Arms

Patients who complete the treatment phase, or discontinue trial treatment for a reason other than disease progression will move into the follow-up phase. The following assessments will be performed every 3 months up until the last patient has completed 24 months of follow-up, until the start of new anti-neoplastic therapy, disease progression, death or end of the study.

- Physical examination
- Vital signs and weight
- Documentation of ECOG performance status
- Laboratory studies including FBE, biochemistry and coagulation, hepatic and kidney function tests (only if clinically indicated)
- Radiological evaluation with a CT Chest/Abdomen and Pelvis or MRI
- Whole body bone scan (only if clinical indicated)
- Response assessment
- Adverse Event assessment
- Blood samples for correlative studies
- New anti-cancer therapy status
- Fresh biopsy sample 3 months after the last dose of SABR if considered safe

8.6 Survival Follow-up

Patients who discontinue trial treatment due to progression, progress during follow-up or commence a new systemic treatment will be followed for survival only. Survival status will be assessed every 3 months until death, withdrawal of consent, or the end of the study, whichever occurs first. Where possible, every effort should be made to record results of subsequent tumour assessments and any new anti-cancer therapies.

8.7 Concomitant Medications

All treatments that the investigator considers necessary for a patient's welfare may be administered at the discretion of the investigator in keeping with the community standards of medical care. All concomitant medication will be recorded on the relevant CRF including

all prescription, over-the-counter (OTC), herbal supplements, and IV medications and fluids. If changes occur during the trial period, documentation of drug dosage, frequency, route, and date may also be included on the CRF.

All concomitant medications received within 28 days prior to randomisation and 30 days after the last dose of trial treatment should be recorded.

8.8 Supportive Care/Rescue Medication

Patients should receive appropriate supportive care measures as deemed necessary by the treating investigator. Suggested supportive care measures for the management of adverse events with potential immunologic etiology are outlined below (table 4). Where appropriate, these guidelines include the use of oral or intravenous treatment with corticosteroids as well as additional anti-inflammatory agents if symptoms do not improve with administration of corticosteroids. Note that several courses of steroid tapering may be necessary as symptoms may worsen when the steroid dose is decreased. For each disorder, attempts should be made to rule out other causes such as metastatic disease or bacterial or viral infection, which might require additional supportive care. The treatment guidelines are intended to be applied when the investigator determines the events to be related to pembrolizumab.

Table 4 Supportive care measure of adverse events of immunologic etiology

Adverse event type	CTCAE version 4.03 Grade	Treatment
Pneumonitis	Grade 2	Treat with systemic corticosteroids. When symptoms improve to Grade 1 or less, steroid taper should be started and continued over no less than 4 weeks. In the event of recurrent grade 2 pneumonitis, pembrolizumab should be discontinued.
	Grade 3-4	For, immediately treat with intravenous steroids. Administer additional anti-inflammatory measures, as needed. Add prophylactic antibiotics for opportunistic infections in the case of prolonged steroid administration.
Diarrhoea/Colitis	General	Patients should be carefully monitored for signs and symptoms of enterocolitis (such as diarrhoea, abdominal pain, blood or mucus in stool, with or without fever) and of bowel perforation (such as peritoneal signs and ileus). All patients who experience diarrhoea/colitis should be advised to drink liberal quantities of clear fluids. If sufficient oral fluid intake is not feasible, fluid and electrolytes should be substituted via IV infusion. For Grade 2 or higher diarrhoea, consider GI consultation and endoscopy to confirm or rule out colitis.
	Grade 2 that persists > 3 days	Administer oral corticosteroids. When symptoms improve to Grade 1 or less, steroid taper should be started and continued over no less than 4 weeks
	Grade 3 or 4 that persists > 1 week	Treat with intravenous steroids followed by high dose oral steroids. When symptoms improve to Grade 1 or less, steroid taper should be started and continued over no less than 4 weeks
Type 1 diabetes mellitus		If new onset, including diabetic ketoacidosis, insulin replacement therapy is recommended
Hyperglycemia	Grade 3-4	If associated with ketosis (ketonuria) or metabolic acidosis, evaluate patients with serum glucose and a metabolic panel, urine ketones, glycosylated haemoglobin, and C-peptide. Insulin replacement therapy is recommended
Hypophysitis	Grade 2	Treat with corticosteroids. When symptoms improve to Grade 1 or less, steroid taper should be started and continued over no less than 4 weeks. Replacement of appropriate hormones may be required as the steroid dose is tapered
	Grade 3-4	Treat with an initial dose of IV corticosteroids followed by oral corticosteroids. When symptoms improve to Grade 1 or less, steroid taper should be started and continued over no less than 4 weeks. Replacement of appropriate hormones may be required as the steroid dose is tapered

Hyperthyroidism or Hypothyroidism	General	Thyroid disorders can occur at any time during treatment. Monitor patients for changes in thyroid function (at the start of treatment, periodically during treatment, and as indicated based on clinical evaluation) and for clinical signs and symptoms of thyroid disorders
	Grade 2 hyperthyroidism Grade 2-4 hypothyroidism	In hyperthyroidism, non-selective beta-blockers (e.g. propranolol) are suggested as initial therapy. In hypothyroidism, thyroid hormone replacement therapy, with levothyroxine or liothyroinine, is indicated per standard of care.
	Grade 3-4 hyperthyroidism	Treat with an initial dose of IV corticosteroid followed by oral corticosteroids. When symptoms improve to Grade 1 or less, steroid taper should be started and continued over no less than 4 weeks. Replacement of appropriate hormones may be required as the steroid dose is tapered.
Hepatic	Grade 2	Monitor liver function tests more frequently until returned to baseline values (consider weekly). Treat with IV or oral corticosteroids
	Grade 3-4	Treat with intravenous corticosteroids for 24 to 48 hours. When symptoms improve to Grade 1 or less, a steroid taper should be started and continued over no less than 4 weeks
Renal Failure or Nephritis	Grade 2	Treat with corticosteroids When symptoms improve to Grade 1 or less, steroid taper should be started and continued over no less than 4 weeks
	Grade 3-4	Treat with systemic corticosteroids. When symptoms improve to Grade 1 or less, steroid taper should be started and continued over no less than 4 weeks.

Management of Infusion related reactions: Signs and symptoms usually develop during or shortly after drug infusion and generally resolve completely within 24 hours of completion of infusion.

Table 5 below shows treatment guidelines for patients who experience an infusion related reaction associated with administration of pembrolizumab.

Table 5: Infusion Related Reaction Treatment Guidelines

CTCAE version 4.03 Grade	Treatment	Premedication at subsequent dosing
Grade 1 Mild transient reaction; infusion interruption not indicated; intervention not indicated	Increase monitoring of vital signs as medically indicated until the patient is deemed medically stable in the opinion of the investigator.	None
Grade 2 Therapy or infusion interruption indicated but responds promptly to symptomatic treatment (e.g., antihistamines, NSAIDS, narcotics, IV fluids); prophylactic medications indicated for <=24 hrs	
Stop Infusion and monitor symptoms. Additional appropriate medical therapy may include but is not limited to:
 
 IV fluids Antihistamines NSAIDS Acetaminophen Narcotics 
Increase monitoring of vital signs as medically indicated until the patient is deemed medically stable in the opinion of the investigator.
 
If symptoms resolve within one hour of stopping drug infusion, the infusion may be restarted at 50% of the original infusion rate (e.g., from 100 mL/hr to 50 mL/hr). Otherwise dosing will be held until symptoms resolve and the patient should be premedicated for the next scheduled dose.
 
Patients who develop Grade 2 toxicity despite adequate premedication should be permanently discontinued from further trial treatment administration
	
Patient may be premedicated 1.5h (\pm 30 minutes) prior to infusion of pembrolizumab with:
 
Diphenhydramine 50 mg po (or equivalent dose of antihistamine).
 
Acetaminophen 500-1000 mg po (or equivalent dose of antipyretic).

Grade 3: Prolonged (e.g., not rapidly responsive to symptomatic medication and/or brief	
Stop Infusion. Additional appropriate medical therapy may include but is not limited to:
 
 IV fluids 	No subsequent dosing

interruption of infusion); recurrence of symptoms following initial improvement; hospitalization indicated for clinical sequelae	Antihistamines NSAIDS Acetaminophen Narcotics Oxygen Pressors Corticosteroids Epinephrine	
Grade 4: Life-threatening consequences; urgent intervention indicated	Increase monitoring of vital signs as medically indicated until the patient is deemed medically stable in the opinion of the investigator. Hospitalization may be indicated. Patient is permanently discontinued from further trial treatment administration.	No subsequent dosing
Appropriate resuscitation equipment should be available in the room and a physician readily available during the period of drug administration		

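### Table 4 reserves steroids for grade 3-4 diarrhoea/colitis lasting more than a week, whereas Table 7 directs them with no such wait

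*Combined protocol and SAP*

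**What the plan says.** Table 4 in Section 8.8 has three entries for diarrhoea/colitis:

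- A general entry covers monitoring, fluids and considering GI consultation and endoscopy. It does not mention steroids.
- The entry labelled "Grade 2 that persists > 3 days" gives oral corticosteroids.
- The entry labelled "Grade 3 or 4 that persists > 1 week" gives intravenous steroids followed by high-dose oral steroids.

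Table 7 in Section 10.1 covers the same event. It withholds pembrolizumab at grade 2 or 3, discontinues it permanently at grade 4, and directs corticosteroids at 1-2 mg/kg prednisone or equivalent followed by a taper, with no duration attached. Its general instruction 3 says that severe and life-threatening immune-related events get intravenous before oral steroid. That instruction sets an order and gives neither a start time nor a wait.

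Section 10.1 refers the reader to Section 8.8 for corticosteroid use. Neither section states which table prevails. Table 4 is offered as suggested care, and Section 8.8 opens with "Patients should receive appropriate supportive care measures as deemed necessary by the treating investigator".

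**The concern.** The Table 4 condition runs backwards on severity, because the more dangerous event has the longer wait. It also stands alone in its own table. For grade 3-4 pneumonitis, for example, the text is "For, immediately treat with intravenous steroids". Taken together, this looks like a drafting slip or outdated text.

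What is at stake is patient safety and consistent care between the two sites. The row includes life-threatening events, and Table 4's general entry itself names bowel perforation as a sign to watch for. Grade 3-4 colitis is one of only two toxicities named in the early termination criteria (Section 14.10). The count for that rule and the grade 3+ tally in Section 14.5 do not depend on when steroids start, because the patient is already at grade 3 or 4.

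**Working it through.** **1. The two tables side by side.**

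| Event | Table 4 (Section 8.8) | Table 7 (Section 10.1) |
|---|---|---|
| Grade 2 | Oral steroids after more than 3 days | Steroids, no persistence condition |
| Grade 3 | IV then oral steroids after more than 1 week | Steroids, no persistence condition |
| Grade 4 | IV then oral steroids after more than 1 week | Steroids, no persistence condition, if the treatment cell is merged; otherwise general instruction 3 only |

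No Table 4 entry lists steroids for a grade 3-4 event during its first week.

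**2. Grade 4 in Table 7.** In the text as extracted, the steroid cell sits on the grade 2-3 line and the grade 4 line is blank. The same blank appears on the more severe line for pneumonitis, hepatic events, nephritis and myocarditis. Read literally, Table 7 would then carry no event-specific treatment for severe pneumonitis or severe hepatitis, so a merged cell is the natural reading. Without relying on it, the direct mismatch is at grade 3, and grade 4 rests on general instruction 3, which states no wait.

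**3. Consistency within Table 4.** Six event types have a grade 3-4 steroid row: pneumonitis, diarrhoea/colitis, hypophysitis, hyperthyroidism, hepatic, and renal failure/nephritis. Only diarrhoea/colitis carries a wait (1 of 6). Against the table's own grade 2 threshold, the wait is 7 days versus 3, and 7/3 = 2.33.

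**4. Is the wait time for diagnosis?** Section 8.8 says its guidelines apply once the investigator has judged the event related to pembrolizumab, so attribution comes before the row is used. Ruling out other causes is a separate instruction: "For each disorder, attempts should be made to rule out other causes such as metastatic disease or bacterial or viral infection". Neither needs a week's delay written into the steroid row.

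**5. Reach.** With n = 32 (Section 14.9) and true rate p, expected cases = 32p and P(at least one) = 1 − (1 − p)^32. Section 14.10 expects grade 3+ pneumonitis and colitis below 5%. The 5% row reproduces the overall figure in Table 9.

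| p | Source | Expected cases | P(at least one) |
|---|---|---|---|
| 5% | Section 14.10 bound, applied to colitis alone | 1.6 | 0.806 (Table 9: 0.806) |
| 2.5% | Assumption: the 5% covers both events, split evenly | 0.8 | 0.555 |
| 2% | Assumption; see the objection on Section 4.12 | 0.64 | 0.476 |
| 1% | Assumption | 0.32 | 0.275 |

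These are ceilings on colitis cases and do not count patients whose steroids would be delayed. The documents give no rate for grade 3-4 diarrhoea without colitis, which the row also covers.

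**The case against.** The strongest reply is that the two instructions can both be followed. Table 4 is suggested care, and Section 8.7 adds "All treatments that the investigator considers necessary for a patient's welfare may be administered at the discretion of the investigator", so nothing prevents earlier steroids. Because Section 10.1 refers to Section 8.8, Table 7 could be read as giving the dose and Table 4 the timing. A site managing a drug-related grade 3-4 case must also consult Table 7 to withhold or stop pembrolizumab, and will meet the steroid instruction there. These points stand as limits on harm. They do not justify a written wait that lengthens with severity, and on the dose-and-timing reading the odd ordering becomes the operative rule.

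Serious adverse event handling is a further safeguard. Grade 4 or hospitalised events are reported within one working day/24 hours, and the coordinating or principal investigator reviews them in real time (Sections 12.3, 12.8.1 and 17.3). A grade 3 event managed without hospitalisation may not qualify, and none of these safeguards says when steroids should start.

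It can also be argued that 5% overstates the reach. The phase I series of 495 patients in Section 4.12 lists only infusion reactions, hypothyroidism and pneumonitis as inflammatory or immune-mediated events above 2%. If colitis was classed that way, its any-grade rate was at most 2%. This is fair, although that was pembrolizumab without SABR and plain diarrhoea may not have been counted. The 2% row above already shows the result.

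Finally, the fix leaves the grade 2 mismatch in place. That is true and deliberate: the case made here rests on the grade 3-4 row.

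**Conclusion.** The concern holds. Table 4 makes steroids for grade 3-4 diarrhoea/colitis conditional on more than 7 days' persistence, while Table 7 states no wait and no precedence is given. The finding is secure at grade 3. At grade 4 it rests on the merged-cell reading of Table 7, or failing that on general instruction 3. This is inconsistent guidance, which falls short of two orders that cannot both be obeyed.

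Expected reach is small: fewer than 1.6 of 32 patients with grade 3+ colitis at the protocol's own bound, and 0.32 to 0.8 at the assumed rates of 1% to 2.5%. No endpoint, sample size, error rate or stopping count changes. It should be corrected because the event is severe and the correction is simple.

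**What to change.** Delete the persistence condition from the Table 4 row, so that its label covers grade 3 or 4 without a wait. Keep the row's treatment text, which already follows the intravenous-then-oral order of Table 7's general instruction 3. The Section 8.8 instruction to look for infection and other causes stays in force. The clinical leads should confirm the change, since it suggests intravenous steroids from onset, and a memo should go to both sites.

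Do not add a general rule that Table 7 prevails. The tables also differ elsewhere, and such a rule would silently change guidance not examined here:

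- **Grade 3-4 hyperthyroidism:** Table 4 says "Treat with an initial dose of IV corticosteroid followed by oral corticosteroids"; Table 7 gives beta-blockers or thionamides (on the same merged-cell reading).
- **Grade 3-4 hepatic events:** Table 4 gives intravenous steroids for 24 to 48 hours; Table 7 gives 0.5-1 mg/kg prednisone or equivalent (again on that reading).
- **Grade 2 diarrhoea:** Table 4 waits more than 3 days; Table 7 sets no condition.

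If a precedence sentence is wanted, confine it to grade 3-4 diarrhoea/colitis.

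The cost is one row label in the next amendment, a check by the clinical leads and a memo to two sites. Visits, data collection, sample size and analysis are unchanged.
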